## 10.2.1.3. Visit 2: Study and Device Training

### Confirm all eligibility criteria has been met from Visit 1.

Prior to use, all devices will be prepared following the instructions in the users' guides. Before distributing to subjects at Visit 2, the CONTOUR® NEXT LINK 2.4 study meters (**US only**)/ CONTOUR® PLUS study meters (**China only**) need to be synchronized with the time on the laptop at the investigational center. Subjects will be instructed not to change the time in these devices. Subjects will be provided a CONTOUR® NEXT LINK 2.4 study

## CIP330 Clinical Investigation Plan 10976639DOC Version D Page 67 of 170 Medtronic

meter (**US only**)/ CONTOUR® PLUS study meter (**China only**) to be used to perform fingerstick (capillary SMBG).

**US only:** The investigational center staff will also have to create an account for the subject in CareLink™ Personal For Clinical Research software (see Investigator Site File for details).

#### Overview of general study procedures

#### **Investigational center staff will:**

- Confirm eligibility
- Randomly assign eligible subjects
- Synchronize time of the CONTOUR® NEXT LINK 2.4 study meter(US only)/ CONTOUR® PLUS study meters (China only) with the time on the investigational center's laptop
- US only: Create an account for the study subjects in CareLink™ Personal For Clinical Research software
- Train subjects on study devices
- Confirm sensor locations according to subject's age (see Sensor Wear Location Table)
- Enter data into eCRFs as appropriate
- Schedule the next visit date and time

## Overview of study devices and supplies

#### Investigational center staff will disburse the following to subjects:

- DS5(s)
- CONTOUR® NEXT LINK 2.4 study meter(s) (US only)/ CONTOUR® PLUS study meters (China only)
- BG supplies (e.g. control solution, batteries, meter strips, and lancets)
- Other study materials (e.g., study reference card, device user guides, and training materials)
- Other study supplies (e.g., DS5 return materials and alcohol swabs)

Investigational center staff will record and track all study devices outlined in the device accountability section (see Section 7.4) on the appropriate eCRF.

10976639DOC Version D Page 68 of 170

### **Overview of training and instructions**

#### **Investigational center staff will:**

- Train each subject on sensor insertions, removal, study devices, and study procedures
  - o Subject will be instructed to wash hands thoroughly with soap and water.
  - Subject will be instructed to clean the insertion site with alcohol and let the insertion site air dry prior to sensor insertion.
- Instruct subjects that additional OTC tape(s) (e.g. Hypafix™\* tape, etc.) may be used if needed
- Train subjects on use of CONTOUR® NEXT LINK 2.4 study meter(US only)/ CONTOUR® PLUS study meter (China only)
  - Subject will be instructed to wash his/her hands thoroughly with warm, soapy water, rinse and dry before testing blood glucose
  - Consider best practice to use "second drop" technique, express first drop and wipe away, express second drop for meter BG testing
  - Subjects will be instructed to use only the CONTOUR® NEXT LINK 2.4 study meter (US only)/ CONTOUR® PLUS study meter (China only) during the course of the study to perform study defined SMBG measurements
  - Subjects will be instructed to perform a quality control (QC) testing when a new vial of test strips is used
- Perform applicable QC testing (CONTOUR® NEXT LINK 2.4 study meter [**US only**]/ CONTOUR® PLUS study meter [**China only**]). Shake control solution bottle well prior to use.
- Instruct subjects to insert sensors in the locations according to their age. Sensors worn in the same insertion site location may be inserted on same side or opposite sides. Sensors may be inserted with the assistance of a caretaker:
  - 14-17 years
    - Arm/Arm/Buttock
    - Buttock/Buttock/Arm
  - 18-80 years
    - Arm/Arm

- Synchronize time on each Disposable Sensor (DS5) worn in-clinic by the subject using the Synergy Download Utility
- Instruct subjects to perform fingersticks (capillary SMBGs)
- Recommend subjects to set alarm (e.g., on their phone) to check their fingersticks (SBMG) at insertion, 2 hours, 10 hours, and 24 hours after insertion on Day 1 and also one approximately at the same time every day as time of the insertion
- Have subject perform the first SMBG at the investigational center or a follow up call will be required to confirm this
- Instruct subjects to wear the devices up to 7-day training period. Instruct subjects to remove the sensors (at end of training period or at investigational center) after 7 days (T= 176-188 hours).
- Instruct subjects during training period that they should spend time bending and twisting even if they don't undergo aerobic exercise.
- Instruct subjects on Disposable Sensor (including the inserter component) return.
- Subjects will be provided information to help identify sensor fracture, breakage or damage (i.e., subject would note a sensor failure and upon removal would see that the sensor electrode is not fully or partially present when removing the sensor)
  - Subjects should notify site immediately of sensor breakage/fracture
  - Site should notify Medtronic when sensor breakage is suspected. (See Section 24 for notification process)
  - Site may provide therapy recommendations for sensor breakage as per investigator discretion (i.e. ultrasound imaging, surgical removal)
- Instruct subjects to contact for technical issues and support:
  - US only: Subjects and/or Sites are to call the 24-Hour Technical Support (TS)
  - o **China only:** Subjects are to call Investigational Center staff
- Remind subjects to bring in the CONTOUR® NEXT LINK 2.4 study meter (US only)/ CONTOUR®
  PLUS study meter (China only) for accuracy testing (with control solution per IFU) to each visit

#### In addition:

 Assess subjects for the occurrence of any adverse events or device deficiencies (see Section 22 and 24 at each visit and document on the appropriate source) and record event(s) on the appropriate eCRF

The main purpose of Visit 2 is to perform random assignment and provide the subjects with study device training that would be comparable to training provided to patients in the actual clinical use. The subjects will receive training on the study requirements before completing the training visit. All subjects will be trained on the device(s) to be used in the study prior to leaving the investigational center. Investigational center staff will train the subjects on the appropriate use of the study devices. Each subject will receive training on sensor

## CIP330 Clinical Investigation Plan 10976639DOC Version D Page 70 of 170 Medtronic

insertion and removal, other study devices, and study procedures. This training includes SMBG. The training is expected to last 15 minutes to 2 hours in duration on average, depending on the subject's experience. Training materials provided to the subject may include instructions for use (IFU)s, Getting Started Guides, and Quick Reference Guide. This allows subject familiarization with study devices and procedures.

Subjects will continue on their current diabetes regimen (including glucose monitoring with their own meter when desired) independent of the study devices.

Subjects will be instructed by the investigational center that they are not to use the study devices (except for the study meter) for the management of their diabetes.

This study will involve random assignment and subjects will not be blinded to the study devices used. However, the data generated from the study devices will be blinded to the subjects.

## **Overview of assignment**

Subjects will be assigned to FST Timing (random assignment) according to their age:

### FST Timing for 14-80 years old:

Group	Sensor Wear Day Timing of FST from Sensor Insertion T=0	
A1	Day 1, 3, 4 and 7	2-10 hours (+2), 50-58 hours (±6), 74-82 hours (±6), 146-154 hours (±6)
A2	Day 1, 3, 4 and 7	10-18 hours (±2), 58-66 hours (±6), 82-90 hours (±6), 154-162 hours (±6)
B1	Day 1, 3, 4 and 7	18-26 hours (±2), 66-74 hours (±6), 90-98 hours (±6), 162-170 hours (-6, +2)
B2	Day 2, 4, 5 and 6	24-32 hours (±2), 74-82 hours (±6), 98-106 hours (±6), 122-130 hours (±6)
C1	Day 2, 4, 5 and 6	32-40 hours (±2), 82-90 hours (±6), 106-114 hours (±6), 130-138 hours (±6)
C2	Day 2, 4, 5 and 6	40-48 hours (±2), 90-98 hours (±6), 114-122 hours (±6), 138-146 hours (±6)

The following is the FST schedule for the subjects according to their age:

## The following is the FST schedule for the subjects according to their age: Subjects 14 - 80 years

- o 4 x 8 hours FST
- Challenges
  - Two Hyperglycemic Challenges
  - Two Hypoglycemic Challenges
  - If challenges are performed, the following are recommended:
    - **US only:** Investigator discretion may be used in selecting which challenge is to be performed for each FST as long as 2 hyperglycemic challenges and 2 hypoglycemic challenges are met.
    - China only: Whether performing recommended challenges or not will be based on Ethics Committee (EC) suggestion and investigator discretion. Absence of challenges during FST will not be considered a protocol deviation.

Subjects will be assigned to sensor location (random assignment) according to their age:

- 14-17 years
  - Arm/Arm/Buttock
  - Buttock/Buttock/Arm
- 18-80 years
  - Arm/Arm

10976639DOC Version D

Page 72 of 170

Medtronic

#### **10.2.1.3.1.** Procedures Including YSI™\* FST Timing and SMBG Requirements

SMBGs that are collected will be used retrospectively for calibration(s) of sensor as applicable.

#### **SMBG Requirements**

- On Day 1, a minimum of 4 fingerstick glucose readings (SMBG) at the times below will be requested with target of 7 total fingerstick glucose readings:
  - o Time = 0 hour
    - Sensor insertions will be performed
    - The 0 hour represents the time after the last sensor has been inserted
  - Time = 2 hours
    - T = 2 hours after the last sensor has been inserted
  - Time = 10 hours
    - T = 10 hours after the last sensor has been inserted
  - Time = 24 hours
    - T = 24 hours after the last sensor has been inserted
- On Day 2-7, a minimum of 4 fingerstick glucose readings (SMBG) per day will be requested with target of 7 fingerstick glucose readings (with one of them occurring at the same time of day as initial sensor insertion [±1 hour]). For example, if sensor was inserted at 8 am, then each day after that one SMBG will done at this same time.
- One SMBG should be taken upon arrival for each FST
- At the end of each FST, take one SMBG.
- Consider best practice to use "second drop" technique: express first drop and wipe away, express second drop for meter BG testing.
- Subjects will be instructed to check SMBG 4-7 times spread throughout the day.

10976639DOC Version D

Page 73 of 170

Medtronic

#### 10.2.1.4. Visit 3: End of Training Period -Investigational Center Visit

## Overview of general study procedures Investigational center staff will:

- Instruct subject to self-remove the sensors that he/she is still wearing at this visit
- Perform a Skin Assessment on the area of each of the sensor insertion sites and document in subject source and complete Skin Assessment eCRFs for each inserted sensor.

#### US only:

- Upload\_CONTOUR® NEXT LINK 2.4 study meter into CareLink™ Personal For Clinical Research software
- Upload Disposable Sensor using Synergy Download Utility Software (following instructions provided)

#### China only:

- Download CONTOUR® PLUS study meter and provide to sponsor
- Upload Disposable Sensor using Synergy Download Utility Software (following instructions provided)
- Determine if additional training is needed (e.g., if the subject is not following finger-stick monitoring requirements). If additional training is required, subjects will be retrained using training materials supplied during training visit 2 and research staff may focus on specific areas of opportunity for improvement.
- Enter data into the eCRFs as appropriate
- Review requirements of next study visit with subjects
- Disburse Disposable Sensor to subjects who will insert at home
- Schedule the next visit dates and times (including the first YSI™\* FST)
- The subject will be instructed to insert sensors. Note: the subject will use the CONTOUR® NEXT LINK 2.4 study meter (US only)/ CONTOUR® PLUS study meter (China only) provided by the Investigational center staff.
- Remind subjects on Disposable Sensor(s) (including the inserter component) return (see Table 1 US Device Accountability Requirements and Table 2 China Device Accountability Requirements)

#### Overview of study devices and supplies

#### Investigational center staff will disburse the following to subjects as needed:

- DS5(s)
- BG supplies (e.g. control solution, batteries, meter strips, and lancets)
- Other study supplies (e.g. DS5 return materials and alcohol swabs)

Investigational center staff will record and track all study devices outlined in the device accountability section (see Section 7.4) on the appropriate eCRF.

The YSI™\* FST visits should be scheduled at this visit by the investigational center staff. The visits will be scheduled so that YSI™\* FST timing and fingerstick glucose reading requirements are conducted as displayed in Section 10.1.

The study coordinator will enter all necessary device return information on the appropriate eCRF and any additional subject visits (unscheduled) on the appropriate eCRF.

In the event the subject no longer wants to participate in the study after the training period or any time throughout the course of the study including the day of last FST, the subject will be withdrawn. This will be documented in the subject study file including the reason for withdrawal and the Exit eCRF will be completed.

#### 10.2.1.5. Visit 4: Phone Call or Optional Office Visit

The purpose of visit 4 (phone/clinic visit) is to verify that the sensor insertion was performed at the appropriate insertion time, insertion location and SMBG reminder.

For Group A1 subjects: this visit may be combined with Visit 5.

For Group A2, B1, B2, C1 and C2 subjects: During the phone call or at the investigational center, the investigational center staff will confirm subject has inserted the sensors at the appropriate time and sensor location. Once the study period sensors are inserted, the subject should follow the YSI™\* FST Timing and SMBG requirements (Section 10.2.1.3.1).

In addition, subjects should be reminded to bring medication, syringes, insulin and infusion sets that might be needed for their personal pumps during the  $YSI^{TM*}$  FST visit. Also, subjects will be reminded on Disposable Sensor (including the inserter component) return.

#### **10.2.1.6.** Visit 5, 7, 9, and **11:** YSI™\* FSTs

The YSITM\* FST is an 8-hour frequent blood glucose sampling session using IV blood samples and a laboratory blood glucose analyzer, YSITM\*. The investigational center staff will set up the YSITM\*. Meals will be provided to the subjects.

Additionally, on Visit 11 reminder that subject should keep the sensor in for at least 176 hours.

10976639DOC Version D

Page 75 of 170 Medtronic

# 10.2.1.6.1. Procedure Guidelines For Subjects Undergoing Observation Only (Visit 5, 7, 9, and 11)

Per investigator discretion Type 1 or Type 2 subjects who do not have an insulin to carb ratio and insulin sensitivity factor at Visit 1 should not undergo hypoglycemic or hyperglycemic challenges but may undergo observation. There are no specific criteria to start the FST.

These subjects should eat and take their insulin at home as per their usual diabetes management prior to coming to clinic.

These subjects should also take any other medications at their usual times both at home and in clinic. Subjects should bring all medications they are taking with them to the clinic, even if they are not scheduled to take that medication that day.

Subjects may exercise during the observation period if their glucose is between 100-300 mg/dL (5-6-16.7 mmol/L).

Insulin (if applicable), medication (if applicable), diet, diabetes monitoring/management and ketone monitoring/management may be performed per Investigator discretion.

# 10.2.1.6.2. Prior to Arrival at the Clinic (Visit 5, 7, 9, and 11) for the Subject Undergoing Challenges

For subjects who undergo hyperglycemic or hypoglycemic challenges, the investigator will provide recommendations for *the night before* and *during* the YSITM\* FST visit in the following areas:

- Food intake
- Medication management
- Glucose target

**China only:** Whether performing recommended challenges or not will be based on EC suggestion and investigator discretion. This section is only applicable if subject undergoes challenge(s).

10976639DOC Version D

Page 76 of 170

# 10.2.1.6.3. Upon Arrival to the Clinic (Visit 5, 7, 9, and 11) for the Subject Undergoing Challenges

Ketones should be in the following range *for those who undergo hypoglycemic or hyperglycemic challenge* as described below:

Subjects may start the challenge when ketone level is less than or equal to  $(\leq)$  0.6 mmol/L.

For example, should a subject arrive with ketone levels greater than (>) 0.6 mmol/L, per investigator discretion, intravenous (IV) or oral hydration may be provided to subject to bring the ketone level down to less than or equal to ( $\leq$ ) 0.6 mmol/L.

Site should also have available during hypoglycemic and hyperglycemic challenge the following:

- IV catheter for IV access of subject
- At least 1000 ml of normal saline for IV fluid hydration
- At least 1000 ml of 5% dextrose for IV use
- 1 mg of Glucagon
- Two 50 ml Ampules of 50% dextrose
- Regular insulin for IV administration

**China only:** Whether performing recommended challenges or not will be based on EC suggestion and investigator discretion. This section is only applicable if subject undergoes challenge(s).

#### 10.2.1.6.4. In-Clinic Procedures

#### **Overview of general study procedures**

#### Investigational center staff will:

- Set up the YSI™\* instruments (see Investigator Site File for details)
- Perform applicable QC testing:
  - US only:CONTOUR® NEXT LINK 2.4 study meter and Precision Xtra™\* ketone meter
  - China only: CONTOUR® PLUS study meter and FreeStyle Optium Neo ketone meter
- Synchronize YSI™\* devices at the investigational center with the designated study clock

10976639DOC Version D Page 77 of 170

- Verify that sensor insertion was performed at the appropriate insertion time, insertion location and SMBG reminders.
- Synchronize time on each Disposable Sensor (DS5) worn in-clinic and at home by the subject using the Synergy Download Utility (Visit 5 only)
- Conduct SMBG testing upon subject arrival
- Refer to Section 10.2.1.3.1 for instructions on Procedures Including YSI™\* FST Timing and SMBG Requirements
- Conduct YSI™\* FST procedures
- Conduct the hypoglycemic or hyperglycemic challenge for subjects with known insulin sensitivity factor and insulin carbohydrate ratio.
  - China only: Whether performing recommended challenges or not will be based on EC suggestion and investigator discretion.
- Following completion of each YSI™\* FST:
  - US only: Upload CONTOUR® NEXT LINK 2.4 study meter into CareLink™ Personal For Clinical Research software
  - o **China only:** Download CONTOUR® PLUS study meter and provide to sponsor
- Upload YSI™\* data to sponsor's secure site
- Calculate time for T=176-188 hours where the sensor may be removed at that time or after that time to ensure that the devices are not removed pre-maturely (**Visit 11 only**)
- Subjects will continue to wear sensors past the end of this visit to achieve sensor wear for T=176-188 hours
- Review requirements of next study visit (phone or EOS visit) with subjects
- Review the next visit date and time for YSI™\* FST (Visits 5, 7 and 9 only)
- Enter data into eCRFs as appropriate
- Subjects should be reminded to bring extra infusion sets for their personal pump to next YSI™\* FST in case they are asked to change them due to occlusion or suspicion of occlusion.
- Remind subject to bring medication, syringes, insulin and infusion sets that might be needed during the YSI™\* FST visit.
- Remind subjects on Disposable Sensor(s) (including the inserter component) return (see Table 1 US Device Accountability Requirements and Table 2 China Device Accountability Requirements)

#### Overview of study devices and supplies

#### Investigational center staff will disburse the following to subjects as needed:

- DS5(s)
- BG supplies (e.g., batteries, meter strips, and lancets)

# CIP330 Clinical Investigation Plan 10976639DOC Version D Page 78 of 170 Mecttronic

Other study supplies (e.g., alcohol swabs)

Investigational center staff will record and track all study devices outlined in device accountability section (see Section 7.4) on the appropriate eCRF.

#### **Overview training and instructions**

#### **Investigational center staff will:**

- Remind subjects to perform fingersticks (capillary SMBG)
- Remind subjects to contact for technical issues and support:
  - o **US only:** Subjects and/or Sites are to call the 24-Hour Technical Support (TS)
  - o China only: Subjects are to call Investigational Center staff
- Fingerstick will be performed at home as stated in Section 10.2.1.3.1.

#### **10.2.1.6.4.1** Blood Glucose Monitoring During the YSI™\* FST

The frequency of blood draws for YSI™\* FST sampling is dependent on the average value of YSI-B and YSI-W probes of the previous sample, according to the following ranges:

- less than (<) 75 mg/dL (4.2 mmol/L); every 5 minutes (window of 3-8 minutes)
- greater than or equal to (≥) 75 mg/dL (4.2 mmol/L); every 15 minutes (window of 7-23 minutes)

#### **10.2.1.6.4.2** YSI™\* FST Not Available (For Example, IV Occlusion)

In the event that YSI™\* blood glucose values are not immediately available, for safety purposes, the investigational center may use the subject's CONTOUR® NEXT LINK 2.4 study meter (**US only**)/ CONTOUR® PLUS study meter (**China only**) to measure glucose. The fingerstick glucose values will be recorded on the appropriate eCRF and not used for analysis.

Venous blood samples should still be drawn for YSI™\* FST.

10976639DOC Version D

Page 79 of 170

Medtronic

#### 10.2.1.6.4.3 Ketone Monitoring

#### **During Challenge:**

- Glucose greater than (>) 300 mg/dL (16.7 mmol/L) every 60 minutes
- Nausea, abdominal pain or vomiting regardless of glucose level

Note: Should be performed with fingerstick only.

Ketone management should be per investigator discretion. This may include oral or IV hydration and insulin management.

# 10.2.1.6.4.4 Procedure Guidelines For Subjects Undergoing Hypoglycemic and Hyperglycemic Challenges

#### **Subject Criteria**

- Only subjects with a known insulin sensitivity factor and insulin carbohydrate ratio (Type 1 or Type 2 subjects) may participate in the hypoglycemic/hyperglycemic challenges.
  - These ratios may be developed for use in study by qualified investigator and can be refined and fine-tuned by investigator
- Subjects without a known insulin sensitivity factor and insulin carbohydrate ratio (Type 1 or Type 2 subjects) will not participate in the hypoglycemic/hyperglycemic challenges, but will participate in the YSI™\* FST with observation only.

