7.9.1.4.6 Other Accuracy Analyses

A correlation between the sensor and YSI[™]* values will be performed. As this statistic ignores any data dependency, it will be used only as a descriptive measure of association.

A linear model, in which YSI[™]* is predicted by sensor values, using a repeated measures model, will be performed. The models solution will provide the intercept and slope, while adjusting for dependence in the data within day. An intercept of 0, along with a slope of 1, would indicate the absence of bias in predicting YSI[™]* from sensor readings. The residuals of the model will be inspected to determine if transformation of either variable is required.

Bland-Altman plots, with 95% confidence interval (CI), will be provided. The paired differences between the sensor and YSI[™]* rating will be plotted against the X-axis reference of mean YSI[™]* and sensor values.

Descriptive subgroup analysis of DS5 sensor performance (20% mean agreement rate (±20 mg/dL [1.1 mmol/L] when SG less than (<) 80 mg/dL [4.4 mmol/L]) will be performed in the following cohorts:

- Diabetes cohorts based on insulin requirement:
 - Type 1 insulin requiring
 - Type 2 insulin requiring
 - Type 2 non-insulin requiring
- Diabetes cohorts based on Centers for Disease Control and Prevention (CDC) classification for younger than 20 years old:

A description of the following 4 groups will be performed:

- Underweight subjects (less than (<) 5th percentile)
- Normal weight subjects (5th percentile to less than (<) 85th percentile)
- Overweight (85th to less than (<) the 95th percentile)
- Obese subjects (greater than or equal to (≥) the 95^{th} percentile)

CIP330 Statistical Analysis Plan		Form
Revision [3.0]	Page 23 of 25	Medtronic

• Diabetes cohorts based on BMI according to WHO criteria [World Health Organization, 2011] for subjects equal to or greater than 20 years old:

A description of the following 5 groups will be performed:

- Underweight subjects (BMI less than (<)18.5 kg/m²)
- Normal weight subjects (BMI 18.5 to 24.99 kg/m²)
- Overweight and obese subjects (BMI 25.00 to 40 kg/m²)
 - Overweight subjects (BMI 25.00 to 29.99 kg/m²)
 - Obese subjects (BMI 30.00 to 39.99 kg/m²)
- Morbidly obese subjects (BMI greater than or equal to (≥)40 kg/m²)
- Diabetes cohorts based on prior real-time CGM experience (by self-report)
 - o CGM naïve
 - CGM experienced
- Diabetes cohorts based on prior pump experience (by self-report)
 - o Pump naïve
 - o Pump experienced

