- Diabetes cohorts based on HbA1c:
 - Baseline HbA1c (by certified National Glycohemoglobin Standardization Program, NGSP, method) will be collected:
 - A description of the following 3 groups will be performed: HbA1c less than (<) 7%, HbA1c 7-9%, HbA1c greater than (>) 9%
 - o Quartile comparison (lowest to the highest) based on HbA1c
- Diabetes cohort based on exercise activity:
 - Per Investigator's discretion, subjects may participate in the exercise in order to obtain low glucose values.

All analyses follow the definitions provided in: Performance Metrics for Continuous Interstitial Glucose Monitoring: Approved Guideline, CLSI POCT05-A [Klonoff et al. 2008].

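### The crude in-clinic agreement rates by insulin requirement and by exercise are confounded by glucose mix, because challenge access depends on having insulin ratios

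*Protocol*

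**What the plan says.** Protocol 10.2.1.6.4.4 sets the rule for challenges: "Only subjects with a known insulin sensitivity factor and insulin carbohydrate ratio (Type 1 or Type 2 subjects) may participate in the hypoglycemic/hyperglycemic challenges". The same list adds: "These ratios may be developed for use in study by qualified investigator and can be refined and fine-tuned by investigator". It then excludes those without ratios: "Subjects without a known insulin sensitivity factor and insulin carbohydrate ratio (Type 1 or Type 2 subjects) will not participate in the hypoglycemic/hyperglycemic challenges". Section 10.2.1.6.1 says of subjects without ratios at Visit 1 that, at the investigator's discretion, they "should not undergo hypoglycemic or hyperglycemic challenges but may undergo observation". Inclusion criterion 4 (9.3) has the same effect.

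For US subjects aged 14-80 with ratios, Section 10.1 provides two hypoglycemic and two hyperglycemic challenges across four 8-hour sessions. The targets in 10.2.1.6.4.4 are about 2 hours below 70 mg/dL and about 2.5 hours at 180-400 mg/dL. Challenges are optional in China (10.1) and absent at ages 2-13 (11.1). Under 10.2.1.6.4.1, blood is drawn every 5 minutes below 75 mg/dL and every 15 minutes otherwise.

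SAP 7.9.1.4.6 and Protocol 25.9.9 plan the 20% / 20 mg/dL agreement rate by cohort, including "Type 2 non-insulin requiring" alongside the two insulin-requiring cohorts. For the exercise cohort they note that "subjects may participate in the exercise in order to obtain low glucose values". SAP 7.9.1.4 applies these descriptive analyses to each of the three primary datasets. No subgroup rate is split by glucose range or challenge status. The error-grid tables in SAP 7.9.1.4.3 are split by YSI range, but not within subgroups.

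**The concern.** An insulin sensitivity factor and a carbohydrate ratio are insulin-dosing parameters, and Visit 1 (10.2.1.2) records them only where applicable. Challenge status will therefore follow the insulin-requirement cohorts closely. Those cohorts then differ by design in how many low and high readings they contain, and the denser sampling below 75 mg/dL widens the difference.

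If accuracy varies by glucose level, two cohorts with the same accuracy at every level will show different crude rates, and a real difference between them can be masked. The exercise cohort has a similar problem. Exercise is used to obtain low values, it may be part of a challenge, and it requires prior investigator agreement and a glucose of 100-300 mg/dL (10.2.1.6.4.5). What is at stake is the interpretation of the planned in-clinic breakdown by insulin requirement and exercise.

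**Working it through.** The plan states no expected rate, size or power for these subgroups, so there is no figure of its own to reproduce. Its one sizing statement (100 subjects, power above 80%) concerns the primary endpoint.

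**Reading counts from the protocol, per subject aged 14-80 with four sessions and all targets met**

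- Hypoglycemic session: 2 h at 5 min = 24 low readings, plus 6 h at 15 min = 24 others, total 48.
- Hyperglycemic session: 8 h at 15 min = 32 readings, of which 2.5 h × 4 = 10 are in the induced high period.
- Total: 2 × 48 + 2 × 32 = 160. Induced low: 48/160 = 30.0%. Induced high: 20/160 = 12.5%.
- Observation only, never below 75 mg/dL: 4 × 8 × 4 = 128 readings, none from a challenge.

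**Effect of mix alone**

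Let L, M and H be the agreement rates in the low, middle and high ranges, identical in both cohorts. Let l and h be the low and high shares of readings in an observation-only subject. The gap (challenged minus observation-only) is

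(low share − l)(L − M) + (high share − h)(H − M).

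The documents give no range-specific accuracy and no natural shares. These are assumed: L 70-92%, M 85-88%, H 80-85%, l 1-3%, h 15-30%.

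- Example with L = 75, M = 88, H = 85, l = 3%, h = 15%. Challenged: 0.30 × 75 + 0.125 × 85 + 0.575 × 88 = 83.7%. Observation-only: 0.03 × 75 + 0.15 × 85 + 0.82 × 88 = 87.2%. Gap −3.4 points before rounding of the two rates.
- Lowest gap: L = 70, M = 88, H = 85, l = 1%, h = 15% gives 0.29 × (−18) + (−0.025) × (−3) = −5.1 points.
- Highest gap: L = 92, M = 85, H = 80, l = 1%, h = 30% gives 0.29 × 7 + (−0.175) × (−5) = +2.9 points.
- L = M = H gives zero.

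**If challenge targets are only partly met (same example)**

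| Challenge time achieved | Readings | Induced low | Induced high | Gap, points |
|---|---|---|---|---|
| Full | 160 | 48 (30.0%) | 20 (12.5%) | −3.4 |
| Half | 2 × (12 + 28) + 64 = 144 | 24 (16.7%) | 10 (6.9%) | −1.5 |
| Quarter | 2 × (6 + 30) + 64 = 136 | 12 (8.8%) | 5 (3.7%) | −0.4 |

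**Natural lows and highs outside the challenges**

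The example gives challenged subjects none. If their other 92 readings carry the same 3% and 15% shares, the low share is (48 + 2.76)/160 = 31.7% and the high share (20 + 13.8)/160 = 21.1%. The gap becomes 0.287 × (−13) + 0.061 × (−3) = −3.9 points, so this simplification does not create the effect.

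**The case against.** A reader might infer that the Type 2 non-insulin-requiring cohort can contain no induced lows or highs. The documents do not support that. Protocol 10.2.1.6.4.4 lets a qualified investigator develop ratios for the study, and observation-only subjects may exercise (10.2.1.6.1), which the SAP describes as a way to obtain low values. Few or probably no challenge readings is as far as the text goes.

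A reader might also infer that the Type 1 against Type 2 contrast is defeated. One challenge rule covers both types, so the rule alone does not undermine the comparison of the two insulin-requiring cohorts.

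The plan also has some safeguards. SAP 7.9.1.4.7 and Protocol 25.9.10 describe the same agreement rate for home-use data by diabetes classification and exercise activity, and challenges take place only in clinic sessions. This helps, but the reference there is the fingerstick meter rather than YSI, and diabetes classification at Visit 1 is recorded as, for example, type 1 or type 2, which need not separate insulin-requiring from non-insulin-requiring type 2. The error-grid tables and iCGM endpoints report range-specific accuracy per dataset, but not by cohort.

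The size is uncertain in both magnitude and sign. Every accuracy rate is assumed, and the protocol says the challenge targets may not always be met. The insulin-requiring cohorts are themselves mixed, because China may omit challenges and ages 2-13 have none. That dilutes the effect in the two pediatric datasets, and it is also a reason to show challenge status.

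**Conclusion.** The crude in-clinic rates by insulin requirement and by exercise are confounded by glucose mix. The problem lies mainly in Dataset 1 and in comparisons involving the Type 2 non-insulin-requiring cohort. Under the stated assumptions, cohorts with identical range-specific accuracy could differ by about −5.1 to +2.9 points. That range illustrates the effect and does not bound it: it rests on assumed accuracies and on full challenge targets. In the worked example the gap shrinks as targets are missed, and it is zero if accuracy is the same in all ranges.

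It would go too far to say that the rates measure glucose mix instead of sensor accuracy, since they reflect both. Nor does the point reach the study's conclusion. The subgroup analyses are descriptive, with no hypothesis attached, and pass/fail rests on the primary endpoints (Protocol 25.9.1, SAP 7.9.1.1).

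**What to change.** In SAP 7.9.1.4.6 and Protocol 25.9.9:

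- Report the insulin-requirement and exercise cohort agreement rates within the YSI ranges already used in SAP 7.9.1.4.3 (40-80, >80-120, >120-240 and >240 mg/dL).
- Show challenge and observation-only sessions separately where both exist.
- Give the number of subjects and of pairs in every cell.
- Add a note that crude cohort rates reflect glucose mix as well as sensor accuracy.

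The cost is SAP and protocol wording and a few extra descriptive tables from data already collected. Some cells will be small or empty. In particular, the challenge column may be empty for the non-insulin-requiring cohort, and there the range-specific rates have to carry the comparison. No clinical procedure changes.
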